12.4. Baseline Assessments

The following data points are to be recorded:

- a) Sex
- b) Age and date of birth
- c) WHO ultrasonography score
- d) Schistosoma mansoni infection intensity by faecal egg count
- e) Praziquantel dose according to standardised WHO dose pole (no later than
- 12 months after the 1st ultrasonography score collection)

12.4.1 Baseline Assessment Assurance following COVID-19 pause

All school-based trial activities were paused on the 19 March 2020 in accordance with the Ugandan government announcement concerning COVID-19. At the time baseline assessments were completed at Buhirigi School except the administration of Praziquantel.

The following data points are to be repeated in at least 10% of the participants from the Buhirigi school cohort to ensure data integrity.

- c) WHO ultrasonography score
- d) Schistosoma mansoni infection intensity by faecal egg count

12.5. Trial assessments following the 1st treatment dose

12.5.1. Timing of assessments

Annual assessments for two years, including treatment efficacy eggs counts at baseline and two-years +4 weeks.

12.5.2. Assessments at time point

The following is to be recorded at around 4-weeks:

Schistosoma mansoni infection intensity by faecal egg count

The following are to be recorded at around 1-year:

a) Schistosoma mansoni infection intensity by faecal egg count (for a subset of 120 participants, 60 per school/community)

The following are to be recorded at around 2-years:

a) WHO ultrasonography score (primary outcome assessment)

ISRCTN Number: 16994599 Page 24 of 48

b) *Schistosoma mansoni* infection intensity by faecal egg count (secondary outcome assessment).

12.5.3. Assessments at the end of trial visit

To be recorded at around 2-years + 4-weeks:

Schistosoma mansoni infection intensity by faecal egg count.

12.6 Schedule of Assessments

[figure not shown]

Figure: Chronological Trial Plan

ISRCTN Number: 16994599 Page 26 of 48

12.7. End of Trial Participation

Participants will return to the standard care of once per annum treatment at the end of the trial.

12.8. Trial restrictions

None

13. Assessment of Safety

13.1. Definitions

13.1.1. Adverse event (AE)

Any untoward medical occurrence in a participant or clinical trial participant administered a medicinal product and which does not necessarily have a causal relationship with this treatment.

An adverse event can therefore be any unfavourable and unintended sign (including an abnormal laboratory finding), symptom, or disease temporally associated with the use of an investigational medicinal product, whether or not considered related to the investigational medicinal product.

Please note: Recording of all adverse events must start from the point of Informed Consent regardless of whether a participant has yet received a medicinal product.

13.1.2. Adverse reaction to an investigational medicinal product (AR)

All untoward and unintended responses to an investigational medicinal product related to any dose administered. All adverse events judged by either the reporting investigator or the sponsor as having a reasonable causal relationship to a medicinal product qualify as adverse reactions. The expression reasonable causal relationship means to convey in general that there is evidence or argument to suggest a causal relationship.

13.1.3. Unexpected adverse reaction

An adverse reaction, the nature, or severity of which is not consistent with the applicable reference safety information (RSI).

When the outcome of the adverse reaction is not consistent with the applicable RSI this adverse reaction should be considered as unexpected.

The term "severe" is often used to describe the intensity (severity) of a specific event. This is not the same as "serious," which is based on participant /event outcome or action criteria.

13.1.4. Serious adverse event or serious adverse reaction (SAE / SAR)

Any untoward medical occurrence that at any dose:

- results in death
- is life-threatening The term "life-threatening" refers to an event in which the subject is at risk of death at the time of the event, not an event that hypothetically might have caused death if it was more severe.
- requires inpatient hospitalisation
- results in persistent or significant disability or incapacity

ISRCTN Number: 16994599 Page 27 of 48

- is an important medical event - Important medical events that may not result in death, be life-threatening, or require hospitalisation may be considered as SAEs when, based upon appropriate medical judgment, they may jeopardise the subject or may require medical or surgical intervention to prevent one of the outcomes listed above. Examples of such events include allergic bronchospasm requiring intensive treatment in an emergency room or at home, convulsions that do not result in inpatient hospitalisation.

13.1.5. Suspected Unexpected Serious Adverse Reaction (SUSAR)

A serious adverse reaction, the nature and severity of which is not consistent with the information set out in the Reference Safety Information

13.1.6. Reference Safety Information (RSI)

A list of medical events that defines which reactions are expected for the IMP within a given trial and thus determining which Serious Adverse Reactions (SARs) require expedited reporting.

The RSI is contained in a clearly identified section of the Summary of Product Characteristics (SmPC) and is the information used for assessing whether an adverse reaction is expected.

For this trial the Reference Safety Information is:

contained in the Table in Section 4.8 of the Summary of Product Characteristics (SmPC) for Praziquantel 600mg tablets (Medopharm Private Ltd) dated May 2021 published by WHOPAR Part 4, available at

https://extranet.who.int/pgweb/WHOPAR/nt008

13.2. Expected Adverse Reactions/Serious Adverse Reactions (AR /SARs)

All expected Adverse Reactions are as specified in section 12.1.6. This must be used when making a determination as to the expectedness of the adverse reaction. If the adverse reaction meets the criteria for seriousness, this must be reported as per section 12.5.

13.3. Expected Adverse Events/Serious Adverse Events (AE/SAE)

The following adverse events are not reported as SAEs

- Adverse events due to malaria.
- Adverse events due to contemporaneous outbreaks of epidemic prone diseases/conditions, including COVID-19 symptoms, occurring from the time of consent to the end of the trial.

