11.1.1.8 Known drug reactions

Neurological

Headaches – very common (>10%)

Dizziness - very common (>10%)

Vertigo, drowsiness – common (1-10%)

Seizures – very rare (<0.01%)

Gastro-intestinal

Gastrointestinal and abdominal pains- very common (>10%)

Nausea – very common (>10%)

Vomiting – very common (>10%)

Anorexia – common (1 – 10%)

Diarrhoea – common (1 – 10%)

Bloody diarrhea - - very rare (<0.01%)

Dermatological

Urticaria – very common (>10%)

Cardiovascular

Unspecified arrhythmias – very rare (<0.01%)

Immune system disorders

Allergic reaction – very rare (<0.01%)

Polyserositis – very rare (<0.01%)

Eosinophilia – very rare (<0.01%)

Jarisch-Herxheimer reaction – very rare (<0.01%)

Hepatobiliary disorders

Liver function tests increased - rare (0.01 - 0.1%)

Musculoskeletal and connective tissue disorders

Myalgia – common (1 – 10%)

General disorders

Fatigue-very common (>10%)

Feeling unwell (asthenia, malaise) – common (1 – 10%)

Fever-common (1 - 10%)

Adverse reactions with food, over the counter drugs or commonly prescribed drugs are not reported.

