13.5. Reporting serious adverse events

The Trial Site Manager will record all adverse events, ensure potential serious adverse events are referred to the trial clinical officer at Kigorobya Health Centre IV and upon confirmation the trial clinical officer report serious adverse events to the Principle Investigator, Chief Investigator, Trial Site Manager and Trial Site co-ordinator using the trial specific SAE form within 24 hours of their awareness of the event.

The Chief Investigator is responsible for ensuring the assessment of all SAEs for expectedness and relatedness is completed and the onward notification of all SAEs to the Sponsor and Merck KGaA (for IMP donated by Merck KGaA) or the manufacturer of biosimilar IMP as required, immediately but not more than 24 hours of first notification. The sponsor has to keep detailed records of all SAEs reported to them by the trial team. The Principal Investigator is responsible for ensuring the onward notification of all SAEs to the Research Ethics Committee in Uganda within 24-hours of first notification.

The Trial Site Co-ordinator is responsible for prompt reporting of all serious adverse event findings to the competent authority of the concerned Member State if they could:

- adversely affect the health of participants
- impact on the conduct of the trial
- alter the risk to benefit ratio of the trial
- alter the competent authority's authorisation to continue the trial in accordance with Directive 2001/20/EC

The completed SAE form can be faxed or emailed. Details of where to report the SAE's can be found on the 'FibroScHot' SAE form and the front cover of the protocol.

Please see Appendix 25.3 at the end of this document for the Safety reporting flow chart.

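### Section 13.3 exempts serious events put down to malaria or current outbreaks from SAE reporting, with no exception for deaths or post-dose events and no standard for the attribution

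*Protocol*

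**What the plan says.** Section 13.3 opens with "The following adverse events are not reported as SAEs" and lists two classes. The first is "Adverse events due to malaria", with nothing further. The second is "Adverse events due to contemporaneous outbreaks of epidemic prone diseases/conditions, including COVID-19 symptoms", and its period is "occurring from the time of consent to the end of the trial".

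Three other sections bear on the same events.

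- **Section 13.1.4** defines a serious event by outcome. An untoward occurrence that "results in death" is serious, with no cause excluded, and convulsions without admission are a named example of an important medical event.
- **Section 13.5** says "The Chief Investigator is responsible for ensuring the assessment of all SAEs for expectedness and relatedness is completed". It also requires all SAEs to be passed on to the Sponsor, the manufacturer and, through the Principal Investigator, the ethics committee.
- **Section 13.2** requires an adverse reaction that meets the seriousness criteria to be reported. It cites the reporting section as 12.5; I read this as the present 13.5.

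**The concern.** The exemption depends on a cause having been assigned, and the assignment is made before anyone away from the site has looked at the event. Section 13.3 does not say who makes it or on what evidence. For COVID-19 it speaks of symptoms, not of confirmed disease.

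The protocol's own lists of praziquantel reactions (6.2.2 and 11.1.1.8) include fever, headache, vomiting, diarrhoea, fatigue, myalgia and seizures. On my reading, each of these could be put down to a febrile or outbreak illness in a child. A serious reaction that is misattributed would therefore fall under the exemption and miss the second opinion that section 13.5 provides for.

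This matters more than usual here. The trial tests more frequent dosing in children. Section 10.4 blinds only the ultrasonographers and the egg-count technicians. Section 19 dispenses with a full data monitoring committee and relies on independent Trial Steering Committee (TSC) members to monitor safety.

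**Working it through.** The plan gives no figure to reproduce on this point, so the check is mainly of the text against itself.

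**1. Limits stated in 13.3.** By outcome: none. By time since dose: none; the outbreak class runs from consent to the end of the trial, so every post-dose period is inside it. By diagnostic confirmation: none. By person responsible for the attribution: none.

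**2. 13.3 against 13.1.4 and 13.5.** A death put down to malaria is serious under 13.1.4. Under 13.5 it belongs to the set of all SAEs to be assessed and notified. Under 13.3 it is not reported as an SAE. No section says which rule prevails.

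**3. What still happens to an exempt event.**
- Section 13.4 has the investigator evaluate each adverse event for severity and relationship to the drug.
- Section 13.4.2 allows the grades unlikely and unrelated only when another documented cause is most plausible.
- Sections 13.4.4 and 13.5 have all adverse events recorded, and 13.5 has potential SAEs referred to the trial clinical officer.

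Local causality grading is therefore kept. What is lost is the assessment of relatedness and expectedness under the Chief Investigator, and the notifications that follow, because these apply to SAEs only.

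**4. A case with two answers.** Suppose a child has a convulsion with fever soon after a dose, and malaria is thought to be the cause.
- Under 13.4.2 a plausible link and a plausible time sequence make the event possibly related, and so an adverse reaction. Section 13.2 then says report.
- If the site also calls the event due to malaria, 13.3 says do not report.
- Section 13.3 does not adopt the documented-cause test of 13.4.2, so nothing in the text prevents both labels from being applied.

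**5. Occasions on which this can arise.** Section 11.1 plans 3, 5 and 9 treatments per child in the control, 2x and 4x arms, including the final treatment. With 200 per arm (17.2):
- control: 200 × 3 = 600
- 2x: 200 × 5 = 1,000
- 4x: 200 × 9 = 1,800
- total: 3,400

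With 750 enrolled, or 250 per arm, the total is 250 × 17 = 4,250. The 4x arm has 9/3 = 3 times the post-dose occasions of control.

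**6. Scale for one listed reaction.** Sections 6.2.2 and 11.1.1.8 give seizures as below 0.01%, without a denominator. If that is per dose (my assumption), the expected number is below 0.0001 × 3,400 = 0.34 in the whole trial and below 0.0001 × 1,800 = 0.18 in the 4x arm. At 4,250 doses it is below 0.43. These are upper limits before any misattribution. No rate is given for malaria or outbreak events, or for misattribution, so the total number affected cannot be computed.

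**7. Effect on the arm comparison.** Let r be the rate of serious reactions per dose and m the share misattributed, both equal across arms.
- Reported reactions per child are 3r(1 − m) in control and 9r(1 − m) in the 4x arm.
- Their ratio is 3 whatever the value of m.
- The absolute difference falls from 6r to 6r(1 − m).

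Events are lost and the absolute excess shrinks, but the ratio does not change.

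**The case against.** The best defence is that 13.3 is an ordinary specific exception to a general rule. In an area where malaria is common (my inference from its being exempted), reporting every such illness as an SAE would bury the useful reports. The safeguards also go beyond those in step 3. The synopsis provides at least one hour of observation and a 24-hour follow-up by a health professional. The independent TSC members monitor safety data, which is not limited to SAEs. No primary or secondary outcome is affected.

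Much of this stands, and it rules out several stronger readings.

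- **That reactions escape causality review altogether.** Sections 13.4 and 13.4.2 apply to every adverse event, exempt or not.
- **That a post-dose convulsion labelled malaria could never become a SUSAR.** If 13.4.2 is applied properly, a presumptive label is not a documented cause, and 13.2 and 13.6 then call for a report. Whether a seizure would count as unexpected depends on reference safety information that is not reproduced in the protocol.
- **That every epidemic disease is exempt.** The text covers contemporaneous outbreaks, though it does not define them.

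The defence does not close the gap. The safeguards in 13.4 rest on the same local judgement that may be wrong. Section 14 treats certain signs within 48 hours as severe adverse reactions automatically, but its list does not include fever or convulsions. Reading 13.3 as an exception to 13.5 also leaves its conflict with 13.2 unresolved. An exemption meant to spare paperwork for common illness does not need to include deaths.

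**Conclusion.** The point holds as a reporting gap and an internal contradiction. Followed as written, one local attribution with no stated standard decides whether a serious event, including a death or an event just after a dose, reaches the Chief Investigator, Sponsor, manufacturer and ethics committee. For an event that is both possibly related and attributed to an exempt illness, 13.2 and 13.3 give opposite instructions.

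The size is unknown and probably small. The one usable rate gives fewer than 0.34 expected seizures at 600 enrolled, if it is per dose. The threefold difference in planned doses means more opportunities for loss in the 4x arm. A reader might infer from this that harm in that arm would be masked or the comparison reversed. The documents do not support that: with equal per-dose misattribution the reported ratio is unchanged, and nothing suggests that misattribution differs by arm.

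Given the safeguards, this should be fixed because the change is cheap and improves oversight. It does not call the trial's conclusions into question.

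**What to change.** Amend 13.3 and reconcile it with 13.1.4, 13.2, 13.4 and 13.5, as follows.

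1. Limit the reporting exemption to events that are neither fatal nor life-threatening and that fall outside a stated post-dose reporting window. Section 14 already uses 48 hours and could supply it. All other serious events go through 13.5 whatever the local attribution.
2. State that 13.2 prevails for any serious event graded at least possibly related.
3. List exempted serious events by arm and time since last dose, with the basis for the attribution, for the independent TSC members. The events are already to be recorded as adverse events, so only the listing and the basis for the attribution are new.

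The cost is a text amendment, matching guidance on the SAE form, and some extra SAE forms for illness that proves unrelated. No visits or tests are added.

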13.4. Evaluation of adverse events

The Sponsor expects that adverse events are recorded from the point of Informed Consent regardless of whether a participant has yet received a medicinal product.

ISRCTN Number: 16994599

Individual adverse events should be evaluated by the investigator. This includes the evaluation of its severity, and relationship to IMP(s)/study treatment (causality).

13.4.1. Assessment of seriousness

Seriousness is assessed against the criteria in section 12.1.4. This defines whether the event is an adverse event, serious adverse event or a serious adverse reaction

13.4.2. Assessment of causality

Definitely: A causal relationship is clinically/biologically certain. **This is therefore an Adverse Reaction**

Probable: A causal relationship is clinically / biologically highly plausible and there is a plausible time sequence between onset of the AE and administration of the investigational medicinal product and there is a reasonable response on withdrawal. **This is therefore an Adverse Reaction.**

Possible: A causal relationship is clinically / biologically plausible and there is a plausible time sequence between onset of the AE and administration of the investigational medicinal product. **This is therefore an Adverse Reaction.**

Unlikely: A causal relation is improbable and another documented cause of the AE is most plausible. **This is therefore an Adverse Event.**

Unrelated: A causal relationship can be definitely excluded and another documented cause of the AE is most plausible. **This is therefore an Adverse Event.**

Unlikely and Unrelated causalities are considered NOT to be trial drug related Definitely, Probable and Possible causalities are considered to be trial drug related

A pre-existing condition must not be recorded as an AE or reported as an SAE unless the condition worsens during the trial and meets the criteria for reporting or recording in the appropriate section of the CRF.

13.4.3. Clinical assessment of severity

Mild: The participant is aware of the event or symptom, but the event or symptom is easily tolerated

Moderate: The participant experiences sufficient discomfort to interfere with or reduce his or her usual level of activity

Severe: Significant impairment of functioning; the subject is unable to carry out usual activities and / or the participant's life is at risk from the event.

13.4.4. Recording of adverse events

Adverse events and adverse reactions should be recorded in the appropriate section of the AE/AR log. Serious Adverse Events and Serious Adverse Reactions should be reported to the sponsor as detailed in section 12.5.

13.5. Reporting serious adverse events

The Trial Site Manager will record all adverse events, ensure potential serious adverse events are referred to the trial clinical officer at Kigorobya Health Centre IV and upon confirmation the trial clinical officer report serious adverse events to the Principle Investigator, Chief Investigator, Trial Site Manager and Trial Site co-ordinator using the trial specific SAE form within 24 hours of their awareness of the event.

The Chief Investigator is responsible for ensuring the assessment of all SAEs for expectedness and relatedness is completed and the onward notification of all SAEs to the Sponsor and Merck KGaA (for IMP donated by Merck KGaA) or the manufacturer of biosimilar IMP as required, immediately but not more than 24 hours of first notification. The sponsor has to keep detailed records of all SAEs reported to them by the trial team. The Principal Investigator is responsible for ensuring the onward notification of all SAEs to the Research Ethics Committee in Uganda within 24-hours of first notification.

The Trial Site Co-ordinator is responsible for prompt reporting of all serious adverse event findings to the competent authority of the concerned Member State if they could:

- adversely affect the health of participants
- impact on the conduct of the trial
- alter the risk to benefit ratio of the trial
- alter the competent authority's authorisation to continue the trial in accordance with Directive 2001/20/EC

The completed SAE form can be faxed or emailed. Details of where to report the SAE's can be found on the 'FibroScHot' SAE form and the front cover of the protocol.

Please see Appendix 25.3 at the end of this document for the Safety reporting flow chart.

13.6. Reporting of Suspected Unexpected Serious Adverse Reactions (SUSARs)

All suspected adverse reactions related to an investigational medicinal product (the tested IMP and comparators) which occur in the concerned trial, and that are both unexpected and serious (SUSARs) are subject to expedited reporting. Please see section 12.1.6 for the Reference Safety Information to be used in this trial.

13.6.1. Who should report and whom to report to?

The Sponsor delegates the responsibility of notification of SUSARs to the Chief Investigator. The Chief Investigator must report all the relevant safety information previously described, to the:

Sponsor

The Principle Investigator in the trial site must report all the relevant safety information previously described, to the:

- Competent authorities in the concerned member states
- Ethics Committee in the concerned member states

The Chief Investigator shall inform all investigators concerned of relevant information about SUSARs that could adversely affect the safety of participants.

13.6.2. When to report?

13.6.3. Fatal or life-threatening SUSARs

All parties listed in 12.6.1 must be notified as soon as possible but no later than **7** calendar days after the trial team and Sponsor has first knowledge of the minimum criteria for expedited reporting.

In each case relevant follow-up information should be sought and a report completed

ISRCTN Number: 16994599

as soon as possible. It should be communicated to all parties within an additional **8** calendar days.

